4.5.1. Analysis of Change in Basal Insulin Dose

Unless otherwise specified, all these analyses will be conducted on efficacy estimand. Descriptive summary statistics will be presented for the change from baseline in basal insulin dose (based on total daily dose) for each treatment at each visit from baseline to Week 30 (double blind period) using the EAS1 and from baseline to Week 52 (double-blind and openlabel periods) using EAS2.

4.5.2. Insulin Sensitivity and β-Cell Function

Unless otherwise specified, all these exploratory endpoints will be conducted on efficacy estimand. For the double-blind period will be conducted using the EAS1. Change from baseline of the following biomarkers: fasting glucagon, C-peptide, insulin, pro-insulin, adiponectin, homeostatic model assessment for β -cell function, and homeostatic model assessment for insulin resistance will be analyzed separately using an MMRM. The MMRM model will be fitted for each biomarker separately with treatment, time, visit-by-time interaction as fixed effect, subject as a random effect, and corresponding baseline as a covariate. The covariance matrix and other model specifications will be similar to those in Section 4.1.5.1. Typically, a log transformation of the biomarkers measure will be used.

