# 4.2. Scientific Rationale for Study Design

This is a superiority study, the main objective of which is to compare the effects of tirzepatide 5 mg and tirzepatide 10 mg QW (pooled), with metformin or basal insulin, or both to those on placebo for glycemic control (defined as change from baseline in HbA1c) in pediatric and adolescent population with T2DM over a 30-week period, followed by a 22-week open-label extension.

The efficacy measure, HbA1c, was chosen as the primary objective because it is an accepted endpoint in glycemic studies in pediatric and adolescent participants with T2DM.

The use of placebo for 30 weeks during the double-blind portion of the study is considered appropriate, as Phase 3 studies with tirzepatide have not been conducted to date in the pediatric and adolescent population. Thus, a placebo comparator is necessary to understand tirzepatide's true safety and efficacy. To protect the safety of the participants enrolled across all arms of this study, the double-blind period is relatively short, there are clear rescue criteria for participants with severe, persistent hyperglycemia (see Section 8.3.3.2) and participants are allowed to decrease basal insulin and/ or metformin as needed if hypoglycemia occurs (for the definition of hypoglycemia, see Section 8.3.3.1).

The doses of tirzepatide for this study were based on efficacy, safety and PK/PD data from two placebo-controlled studies in adults with T2DM, SURPASS-1 (GPGK), monotherapy study versus placebo and SURPASS-5 (GPGI), add-on to basal insulin vs placebo.

To mitigate the occurrence of GI AEs and permit time for the development of tolerance to GI effects, a dose escalation scheme will be used that starts at a low dose of 2.5 mg QW for 4 weeks and then escalates 2.5 mg increments every 4 weeks (Section 6.5.1). Therefore, it will take 4 weeks of dosing to reach a maintenance dose of 5 mg and 12 weeks to reach a maintenance dose of 10 mg.

The background therapies of diet and exercise, with metformin or basal insulin or both, are considered appropriate, as these are approved treatments for pediatric and adolescent participants with T2DM in the US, EU, and many countries around the world.

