To assess the effect of 5 and 10 mg tirzepatide QW, analyzed as pooled and separate treatment arms, on patient-reported outcomes at 30 and 52 weeks	Change from baseline for EQ-5D-Y
 To assess the effect of 5 and 10 mg tirzepatide QW, separately and pooled, at Weeks 8, 16, and 30 on additional metabolic measures 	Measures of insulin resistance, alpha cell and beta cell function, and serum adiponectin

Abbreviations: AEs = adverse events; BMI = body mass index; FSG = fasting serum glucose; HbA1c = glycated hemoglobin; PedsQL = Pediatric Quality of Life Inventory; QW = once weekly; SDS = standard deviation score.

Primary estimands

The primary and each key secondary efficacy analysis will be guided by the "efficacy" estimand and the "treatment regimen" estimand.

Efficacy estimand

The clinical question of interest for the efficacy estimand is the treatment difference between tirzepatide and placebo after 30 weeks of intervention in pediatric and adolescent participants with T2DM, prior to intervention discontinuation for any reason or initiation of rescue antihyperglycemic medication.

Efficacy estimand attributes

- *Population:* Pediatric and adolescent participants with study condition/disease who received at least 1 dose of study treatment.
- *Treatment condition:* The randomly assigned treatment without the influence of rescue antihyperglycemic medication.
- *Endpoints:* The primary and key secondary endpoints will be studied. Further details on the endpoints can be found in the Objectives and Endpoints table (Section 1.1).
- *Population level summary:* The difference in mean change from baseline to 30 weeks will be used for continuous endpoints; the difference in proportion (absolute or relative, as appropriate) will be used for dichotomous endpoints. The population level summary will be conducted using the EAS1.

- *Intercurrent events:* The 2 intercurrent events "intervention discontinuation for any reason" and "initiation of rescue medication" are both addressed by the treatment condition of interest attribute. There are no other intercurrent events.
- *Rationale:* The efficacy estimand aims to evaluate the efficacy under the ideal condition that all participants would adhere to the randomly assigned study intervention and without being confounded by the initiation of new antihyperglycemic medications.

Treatment-regimen estimand

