4.1.5. Analytical Methods

4.1.5.1. Analysis Relative to Efficacy Estimand

The analysis related to the efficacy estimand from double-blind period (baseline to week 30) will be conducted utilizing data in the EAS1 and from double-blind and open-label periods (baseline to week 52) will be conducted using the data in the EAS2.

For double-blind period, the analysis model for continuous measurements to make mean comparisons *over time* among treatment arms relative to the efficacy estimand will be an MMRM. The response variable of the MMRM model will be the change from baseline of the endpoint. Unless specifically provided, the terms in the model are:

- treatment (placebo, tirzepatide 5 mg, and tirzepatide 10 mg) as a factor
- visit, as discrete time
- treatment-by-visit interaction
- baseline age group (10 to 14 years, or 15 to <18 years) as a factor
- baseline antihyperglycemic medication (metformin only, or basal insulin only, or metformin and basal insulin) as a factor, and
- baseline of the endpoint as a covariate.

Restricted maximum likelihood will be used to obtain model parameter estimates and the Kenward-Roger option will be used to estimate denominator degrees of freedom. A linear contrast, averaging estimates from the individual tirzepatide doses at 30-week visit, will be used to estimate the treatment effect of the combined tirzepatide arms compared with placebo.

An unstructured covariance matrix will be used to model the within-patient errors. If this model fails to converge, the following covariance structures will be tested in order:

- Heterogeneous Toeplitz
- Heterogeneous First Order Autoregressive
- Heterogeneous Compound Symmetry
- Toeplitz
- First Order Autoregressive, and
- Compound Symmetry.

The first covariance structure that converges will be used. For double-blind and open-label periods, a similar MMRM model will be used except with below treatment as a factor:

• treatment (placebo/tirzepatide 5 mg, tirzepatide 5 mg/5 mg, and tirzepatide 10 mg/10 mg)

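### SAP 4.5.2 lists a redundant visit-by-time term and no treatment-by-visit term, so read literally the exploratory biomarker model gives one treatment effect for all visits, not effects at Weeks 8, 16 and 30

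*SAP*

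**What the plan says.** SAP Section 4.5.2 covers seven measures: fasting glucagon, C-peptide, insulin, pro-insulin, adiponectin and the two homeostatic model indices. Change from baseline in each is to be analysed by an MMRM "fitted for each biomarker separately with treatment, time, visit-by-time interaction as fixed effect, subject as a random effect", with the matching baseline as covariate. It then adds: "The covariance matrix and other model specifications will be similar to those in Section 4.1.5.1".

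The general MMRM in SAP Section 4.1.5.1 opens its list of terms with "Unless specifically provided, the terms in the model are". That list contains treatment, "visit, as discrete time", "treatment-by-visit interaction", age group, baseline antihyperglycemic medication and baseline. It specifies an unstructured within-patient covariance, with an ordered fallback list if the model fails to converge.

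The objective served is in the tertiary/exploratory part of SAP Section 1.1: the effect of the 5 mg and 10 mg doses, "separately and pooled, at Weeks 8, 16, and 30 on additional metabolic measures". Protocol Section 3 states the same objective.

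On escalation, Protocol Section 4.2 says it takes "4 weeks of dosing to reach a maintenance dose of 5 mg and 12 weeks to reach a maintenance dose of 10 mg". Protocol Section 6.5.1 gives the steps as 2.5 mg every 4 weeks from a 2.5 mg start.

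**The concern.** An MMRM gives a treatment effect at a named visit only if treatment is allowed to interact with visit. The list in Section 4.5.2 has an interaction, but it pairs visit with time, which are two names for one factor. No listed term lets the treatment difference change between visits.

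At stake is whether the pre-specified model answers its own objective. A programmer who follows the sentence exactly obtains one effect per dose over all visits. A programmer who takes it as a slip obtains three. A pre-specified analysis should not leave that choice open. The same sentence also leaves unclear whether the stratification factors are in the model, and it places a random subject effect beside a covariance that is already unstructured.

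**Working it through.** The plan gives no figure for this analysis, so there is none to reproduce. The check is a parameter count and a reading of the sections side by side.

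**Inputs.** Three arms (SAP Section 4.1.4); three post-baseline visits, Weeks 8, 16 and 30 (SAP Section 1.1, matching the fasting sampling visits in the Protocol Section 1.3.1 schedule); the terms in SAP Section 4.5.2; visit defined as discrete time in SAP Section 4.1.5.1.

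**Step 1: what the listed terms can fit.**
- Main effects: intercept 1 + treatment (3 − 1) + time (3 − 1) + baseline 1 = 6 parameters.
- Adding visit-by-time: the product of the indicators for visit j and time k is zero when j ≠ k and equals the time-k indicator when j = k. It adds 0, so the total stays at 6.
- Adding treatment-by-visit instead: (3 − 1) × (3 − 1) = 4, giving 10.

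A numerical rank check on a design matrix with 30 participants in each of three arms gave 6, 6 and 10. Entering time as continuous weeks beside a visit factor also left the rank at 6, so that reading does not rescue the term.

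**Step 2: the contrast at each visit.** As written, the mean for arm a at visit j is μ + α_a + τ_j + β × baseline. For 10 mg minus placebo:

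(μ + α_10 + τ_j) − (μ + α_P + τ_j) = α_10 − α_P,

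which does not depend on j. The numerical check confirmed that the contrast vector is identical at Weeks 8, 16 and 30. With treatment-by-visit terms γ_aj the contrast becomes (α_10 − α_P) + (γ_10,j − γ_P,j), which can differ by visit. The same holds for 5 mg minus placebo and for the pooled average of the two.

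**Step 3: against the objective.** SAP Section 1.1 names three weeks, and two doses plus their pool: 3 × 3 = 9 contrasts with placebo. The model as written has two free treatment parameters, so it offers three contrasts (5 mg, 10 mg, pooled), each the same at every week.

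**Step 4: against the dosing schedule.** Steps of 2.5 mg every 4 weeks put both active arms on 2.5 mg in the first four weeks and 5 mg in the second four. The 10 mg arm then moves to 7.5 mg and reaches 10 mg after 12 weeks. Scheduled doses before the Week 8 visit are therefore the same in both arms. The ±7-day window could let one 7.5 mg dose precede a late visit in some participants. A 10 mg versus 5 mg difference that is constant over Weeks 8, 16 and 30 does not fit this design.

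**Step 5: does Section 4.1.5.1 repair the list?** Its terms are a default that gives way where others are specifically provided, and Section 4.5.2 provides its own. The cross-reference names the covariance matrix and other specifications, and it comes after the effects have been listed. The natural reading is that it covers what the list left open.

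**Step 6: the random subject effect.** A random intercept adds a constant variance to every element of the within-patient covariance. An unstructured matrix already absorbs that constant, so the intercept variance is not separately identified. The implied marginal covariance is unchanged, and so would be the treatment estimates.

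**The case against.** The strongest reply is that this is one wrong word. Two labels for one factor and no treatment interaction is what results if visit-by-time was typed for treatment-by-time, and the next sentence points to a section that contains the right term. That is probably what happened, and a sensible programmer might restore it. It does not settle the text, because the general list yields to specific ones.

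Some stronger readings are tempting and should be resisted.
- A reader might infer that effects at the three weeks cannot be estimated at all. The model runs, the samples are scheduled at those visits, and the general MMRM would give the effects. Only the literal Section 4.5.2 model does not.
- A reader might infer that the Week 30 effect would be understated and the Week 8 effect overstated. That needs effects that grow over time, and the documents give no time course for these measures. Under an unstructured covariance the common effect is also weighted by the inverse covariance, so a simple average over visits is not what the model returns.
- A reader might infer that a false dose difference would be reported at Week 8. The literal model gives no separate Week 8 estimate, and a correct model would also show some chance difference there.
- A reader might infer that the stratification factors were deliberately dropped. They may be among the specifications carried over from Section 4.1.5.1, and Protocol Section 9.3.2.3 says they enter all models, although the SAP supersedes the protocol's statistical text. This is ambiguity, not an established omission.

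The by-visit laboratory summaries in SAP Sections 4.6 and 4.6.3 are a partial mitigation. They are descriptive, use the safety sets rather than EAS1, and do not clearly cover the homeostatic indices.

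**Conclusion.** The point holds for the sentence as written. Visit-by-time adds 0 degrees of freedom, the 4 needed for visit-specific treatment effects are absent, and the stated model does not deliver its stated objective. This rests on visit and time being one factor, as Section 4.1.5.1 defines them, and on the explicit list taking precedence over the default.

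No bias figure should be attached, because size and direction depend on a time course and covariance that the documents do not give. The random subject effect is a redundancy with no demonstrated effect on the estimates.

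The reach is small. The seven measures are exploratory, carry no type I error control (SAP Sections 2.1 and 4.5), and have no bearing on the primary or key secondary analyses. It is a correction worth making because it is cheap and removes a choice from programming.

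**What to change.** In SAP Section 4.5.2:
- Replace the visit-by-time interaction with a treatment-by-visit interaction, and call the time factor visit throughout.
- State that treatment contrasts with placebo (5 mg, 10 mg and pooled) are reported at Weeks 8, 16 and 30.
- State that age group and baseline antihyperglycemic medication are included as in Section 4.1.5.1.
- Delete the random subject effect and leave the within-patient covariance to Section 4.1.5.1.

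The cost is one revised sentence. The model is already specified for the other continuous endpoints, and no new data or method is needed.

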4.6. Safety Analyses

The definitions of AE, SAE, and product complaint can be found in Section 10.3, Appendix 3 of Protocol GPGV.

AEs will be coded from the actual term using MedDRA and reported with PTs and SOC. Selected notable AEs of interest may be reported using HLTs or SMQs.

A TEAE is an untoward medical occurrence that emerges during a defined treatment period, having been absent pretreatment, or worsens relative to the pretreatment state, and does not necessarily have to have a causal relationship with the treatment. For events with a missing severity during the baseline period, it will be treated as "mild" in severity for determining treatment emergence. Events with a missing severity during the postbaseline period will be treated as "severe" and treatment emergence will be determined by comparing with baseline severity.

In general, the baseline of a TEAE is defined as an event prior to first dose of randomized study treatment (tirzepatide or placebo). MedDRA LLT will be used in the treatment-emergent derivation. The maximum severity for each LLT during the baseline period, including ongoing medical history, will be used as baseline severity.

For participants who are randomized to placebo/tirzepatide 5 mg treatment arm at Week 0, the baseline for overall study safety (including all treatment periods and follow-up period) will be defined as:

- for TEAE: an event starts prior to and is ongoing at the time of the first dose of tirzepatide.
- for lab/vitals/ECG categorical analyses: the last non-missing observation collected prior to the time of first dose of tirzepatide.

Unless specified otherwise, safety assessments will be guided by the *safety estimand* setting comparing safety of tirzepatide doses with placebo irrespective of adherence to study intervention or initiation of rescue therapy. Safety analyses for the double-blind period will be conducted using the SS1. For overall study safety, including double-blind period, open-label period, and safety follow-up period, summary statistics will be provided using the SS2.

Percentages of participants with TE abnormal, high, or low laboratory measures at any time will be summarized and compared between treatment groups using Fisher's exact test.

A TE high value is defined as a change from a value less than or equal to the high limit at baseline to a value greater than the high limit at any time during double-blind period, open-label period, and safety follow-up. A TE low result is defined as a change from a value greater than or equal to the low limit at baseline to a value less than the low limit at any time during double-blind period, open-label period, and safety follow-up. High and low laboratory limits will be determined by the central laboratory reference ranges.

Values and change from baseline to postbaseline values of central laboratory measures, vital signs, and selected ECG parameters will be summarized at each scheduled visit. The analysis model to make comparisons among treatment groups, relative to continuous change from baseline values assessed over time can be found in Section 4.1.5.4.

For special safety topics, in case of a smaller number of events, a listing will be provided instead of summary table.

4.6.1. Compliance and Extent of Exposure

Treatment exposure duration is defined as the time from the first dose until the time of the last dose for a given participant. Missing first dosing date will be replaced with the randomization date. Missing last dosing date will be replaced with the date the patient discontinued treatment or completed the treatment period, whichever is earlier.

Duration of follow-up is defined as time in days from date of randomization to date of safety follow-up or last study visit. Duration on study treatment is defined as time in days from date of first dose of study treatment to date of last dose of study treatment plus 7 days.

Overall treatment compliance will be defined as taking at least 75% of the scheduled doses. Compliance will be calculated by taking the number of doses administered, regardless of the actual dose administered, divided by the total number of doses expected to be administered ×100.

A listing of patients who missed ≥ 3 consecutive doses may be produced. Treatment compliance will be summarized descriptively by treatment using mITT population. Summary of duration of study in double-blinded period, open-label period and, and the follow-up period, and summary of duration on study treatment will be provided by treatment group using mITT.

4.6.2. Adverse Events

Percentages of patients with TEAEs, overall, common, and by maximum severity will be summarized using MedDRA PT. Common TEAEs occurred in ≥5% of patients before rounding in any treatment group will be summarized; maximum severity for the MedDRA PT is the maximum postbaseline severity observed from all associated LLTs mapping to the MedDRA PT. The maximum severity will be determined based on the nonmissing severities. If all severities are missing for the defined postbaseline period of interest, it will be shown as missing in the table. Only counts and percentages will be included for the TEAEs by maximum severity.

Statistical comparisons will be applied at both the SOC and PT levels and risk differences, 95% CIs will be presented. Events will be ordered by decreasing frequency within SOC. For events that are sex-specific, the denominator and computation of percentages will include only patients from the given sex.

Patient narratives will be provided for all patients who experience any of the following "notable" events:

- death
- SAE
- permanent discontinuation of study treatment due to an AE, or
- pregnancy.

An overview of the number and percentage of patients with a TEAE, SAE, and discontinuation from the study or from study treatment due to an AE, as well as the relationship to study treatment will be summarized by treatment from baseline to Week 30 (double-blind period) using SS1, and from baseline to the safety follow-up using SS2. Fisher's exact test will be used to compare the treatment groups for double-blind period.

The number and percentage of patients who prematurely discontinue the study treatment due to an AE will be summarized by treatment using MedDRA PT nested within SOC from baseline to Week 30 and from baseline to the safety follow-up period. Events will be ordered by decreasing frequency within SOC.

4.6.2.1. Deaths

A listing of deaths will be provided using SS2. The listing will include patient identification including the treatment, site number, date of death, age at the time of enrollment, sex, associated AE, time from first dose of study drug to death, time from last dose of study drug to death, cause of death as reported by the investigator.

4.6.2.2. Other Serious Adverse Events

The number and percentage of patients who experienced an SAE during the double-blind period, open-label period, and the follow-up period will be summarized by treatment using MedDRA PT nested within SOC.

Listings of all SAEs will be provided. For the double-blind period, open-label period and the follow-up period, the listing will include treatment, patient identification including the site number, date of the event, age at the time of enrollment, sex, MedDRA SOC and PT, severity, outcome, relationship to study drug, time from first dose of study drug to the event, and time from most recent dose to the event (if the patient discontinued study drug prior to the event).

